#### Visit 6 (End of study- 24 hours to 1 week after visit 5)

- Pt arrives to CTRC – MUH after an 8 hour fast
- Pre – bronchoscopy spirometry (pre- and post-bronchodilator) (safety assessment)
- Pre-bronchoscopy questionnaires: ACQ, ACT, and pre-bronchoscopy safety checklist
- A brief physical exam will be completed
- Urine pregnancy test in females of child-bearing potential (i.e. women who are not at least 1 year post-menopausal or who have not undergone a surgical sterilization procedure).
- Tongue scrape x microbiome
- Bronchoscopy for a) brushings , b) BAL, c) endobronchial biopsies; d) microbiome
- Blood x plasma collection Urine x PGD2 metabolites and isoprostanes
- Exhaled NO (No food, drink (other than water), or strenuous exercise 1 hour prior to visit)
- Stool x microbiome
- Post bronchoscopy spirometry

#### Phone call visit T3 (1 week after the 2nd bronchoscopy)

- ACQ
- Review any concerns, healthcare utilization.

Following the initiation of the study treatment, a  $\pm$  5 days schedule variance will be allowed for subsequent study evaluations.

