### 5.2 Description of the Study Design

Potential subjects will be recruited from the Asthma Institute registry and the CTSI registry, and throughout the community at large. After an initial screen visit, those who sign the consent and meet eligibility will proceed to have methacholine testing; subjects with a > 12% bronchodilation in FEV1, or achieving a 20 % reduction in FEV1 from baseline (PC20) after methacholine, will receive **NOx + CLA** for a period of 8 weeks.

\* 15Nox dose will be taken 24 hours prior to V6 bronchoscopy

\*\*An additional visit might be needed in some participants to perform pre- and post-spirometry after an adequate medication withhold

Prior to treatment, participants will undergo a baseline bronchoscopy at UPMC Montefiore, after which they will be instructed to begin taking the assigned intervention for 8 weeks. At the completion of the treatment period, participants will undergo a second methacholine challenge and a final bronchoscopy.

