- The research coordinator will contact the subject 24-48 hours prior to Visit 3 in order to verify the medication withhold and readiness for the bronchoscopy procedure.
- Pt arrives to CTRC – MUH after an 8 hour fast
- Urine pregnancy test in females of child-bearing potential (i.e. women who are not at least 1 year post-menopausal or who have not undergone a surgical sterilization procedure).
- A physical exam will be completed
- The subject must have used less than 16 puffs of albuterol in the last 48 hours in order to proceed with bronchoscopy procedures
- Pre – bronchoscopy spirometry (pre- and post-bronchodilator) (safety assessment)
- Asthma Control Questionnaire (ACQ)& pre-bronchoscopy safety checklist
- Tongue scrape x microbiome
- Bronchoscopy for a) brushings , b) BAL, c) endobronchial biopsies; d) microbiome
- Blood work for metabolic syndrome ( fasting blood glucose, insulin levels, serum creatinine) lipid profile (HDL, triglycerides, total cholesterol, LDL and VLDL), CBC with differential, and Hgb A1C.

- Plasma collection
- Urine collection X Prostaglandin D2 (PGD2) metabolites and isoprostanes
- Exhaled NO (No food, drink (other than water), or strenuous exercise 1 hour prior to visit)
- Stool x microbiome
- Post bronchoscopy spirometry
- Dispense study drug supply- 4 week supply
- Distribute study Diary Card and review instructions

Phone call visit T1 (2 weeks after Visit 3)

- Review diaries & compliance
- ACQ
- Review any concerns and health care utilization

Visit 4 (4 weeks after Visit 3)

- Short Physical Exam
- Review of diaries and compliance
- Niox Mino (No food, drink (other than water), or strenuous exercise 1 hour prior to visit)
- Pre and Post spirometry
- ACQ & ACT
- Dispense 4 week supply of study drug

Visit 4A (if necessary)

If it is determined by the study coordinator at Visit 4 that the subject has not taken at least 75% of the study drug, the coordinator will provide a 1 week supply of the study drug and ask the subject to return to the Asthma Institute for a compliance check (visit 4A). If the subject is not compliant at Visit 4A, the subject will be withdrawn from the study. If the subject has improved compliance after 1 week, the remaining 3 week supply of the study drug will be dispensed.

Phone call visit T2 (6 weeks after Visit 3)

- Review diaries & compliance
- ACQ
- Review any concerns and health care utilization

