#### Visit 5 (after 8 weeks of treatment)

- ACQ
- Urine pregnancy test in females of child-bearing potential
- Exhaled nitric oxide test
- Brief physical exam
- Methacholine testing- This is a common test often used to confirm a diagnosis of asthma. Methacholine is a chemical that causes the airways to react (narrow) and is easily reversed with the administration of albuterol. Prior to the test, a urine pregnancy test will be performed on women of childbearing potential and a blood pressure reading will be taken. An exhaled nitric oxide test and a brief physical exam will also be performed. The challenge test consists of inhaling very low, but increasing doses of methacholine through a nebulizer to assess how quickly the airways narrow. Spirometry (focusing on the FEV-1) will be performed approximately 30 and 90 seconds after each dose to look for changes in lung function. If/when a 20% decrease in spirometry (FEV-1) is observed the challenge test will be stopped. Multiple measures are in place to perform this test safely and comfortably. Subjects will receive albuterol after the test is done.
- Patient is instructed to take Nitrogen 15 sodium nitrate and 15 sodium nitrite in substitution of regular NOx supplements (same dose) with food approximately 12 h prior to bronchoscopy. This dose is in a form that is easily observed in study samples.
- Dispense study drug supply

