## **7.4 Criteria for Initiating Treatment**

### Inclusion criteria

No exacerbations during the run in. Patients, who exacerbate during the run-in, may re-enroll 4 weeks after the exacerbation has resolved (completed course of systemic corticosteroids).

Completed 1st bronchoscopy and absence of complications or serious adverse events following the procedure (i.e. hospitalizations)

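### The 56-day drug supply is shorter than the visit window allows, so a late Visit 5 can put the only post-treatment methacholine challenge 4 to 5 days off drug

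*Combined protocol and SAP*

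**What the plan says.** **Supply.** Section 6 lists "Dispense study drug supply- 4 week supply" at Visit 3 and "Dispense 4 week supply of study drug" at Visit 4. Visit 4A, used when a participant "has not taken at least 75% of the study drug", splits the second four weeks into one week plus three and adds nothing. The next supply is the final Visit 5 item, "Dispense study drug supply", with no amount. It follows the exhaled NO test and the methacholine challenge in the list.

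**Timing.** Visit 4 is four weeks after Visit 3, and Visit 5 comes after eight weeks of treatment. A variance of plus or minus "5 days schedule variance will be allowed for subsequent study evaluations" once treatment has begun. Visit 6 is 24 hours to one week after Visit 5.

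**First dose.** The day is not fixed. Section 5.2 has participants undergo the baseline bronchoscopy, "after which they will be instructed to begin taking the assigned intervention for 8 weeks". Section 7.4 first requires "absence of complications or serious adverse events following the procedure".

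**Dose recording.** A diary card is issued at Visit 3. Diary and compliance reviews are listed at T1, Visit 4 and T2 (week 6), but not at Visit 5 or Visit 6. Diary review appears again only at the End of Study Visit for withdrawn participants. Section 9.3 describes compliance calls in general terms.

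**Role of the challenge.** The change in methacholine PC20 is the basis for n=12 (Section 8.1). Section 9.1.1 describes the challenge as primarily a check that the combination does not increase airway hyperresponsiveness. It is done after treatment at Visit 5 only.

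**The concern.** This is a single-arm, pre/post study, so its contrast is off drug at baseline against on drug at follow-up. The plan intends dosing to continue to the end: drug is dispensed again at Visit 5, and the labelled dose before the second bronchoscopy replaces that day's regular nitrate and nitrite. Undosed days before Visit 5 would therefore be an unplanned interruption, and a site could produce one while following the supply and window rules exactly.

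The exposed measure is the methacholine challenge. If it is done off drug, it could understate a benefit, or understate a harm that the challenge is there to detect. With 12 participants, a few affected results could matter. Because no diary or dose review is listed at Visits 5 or 6, the affected participants might also be hard to identify afterwards.

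**Working it through.** **The plan's own figure.** Section 8.1 gives n=12 from an effect of 3.8, SD 1.9, two-sided alpha 0.05 and 90% power. The two-group normal formula gives 2 × (1.960 + 1.282)² × (1.9/3.8)² = 5.25, so 6 per group and 12 in total, which matches. The supply point does not depend on this figure. It shows only that the challenge is the measure on which the size rests.

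**Inputs for the supply count.** Visit 3 is day 0. One dose is taken per day (Section 5.3) with full adherence. Supply is 28 + 28 = 56 doses. Visit 4 falls on days 23 to 33 (28 ± 5) and Visit 5 on days 51 to 61 (56 ± 5), giving 11 × 11 = 121 date pairs. Unused capsules are kept, since no return rule is stated. A gap means complete undosed days immediately before Visit 5.

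**Worst case (Visit 5 on day 61)**
- First dose day 1, Visit 4 by day 29: last dose day 56, undosed days 57 to 60, a gap of 4.
- First dose day 0, Visit 4 by day 28: last dose day 55, undosed days 56 to 60, a gap of 5.
- Doses needed through day 60 are 60 or 61 against 56 supplied, a shortfall of 4 or 5.

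**All permitted date pairs**

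| First dose | Gap 1 day | 2 | 3 | 4 | 5 | Any gap | No gap |
|---|---|---|---|---|---|---|---|
| Day 1 | 10 | 9 | 8 | 7 | 0 | 34 | 87 |
| Day 0 | 10 | 9 | 8 | 7 | 6 | 40 | 81 |

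Check: 7×4 + 3+2+1+0 = 34, and 6×5 + 4+3+2+1+0 = 40. These are counts of schedules, not probabilities.

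**What shrinks or moves the gap.** With Visit 4 on time, each missed dose whose capsule is kept shortens the worst-case gap by one day, so 4 or 5 missed doses remove it. A Visit 4 on day 33 moves the whole gap to before Visit 4: days 29 to 32 (4 days) or 28 to 32 (5 days).

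**Anchor.** If Visit 5 is counted from the first dose and that dose is on day 1, the latest Visit 5 is day 62 and the gap is 5 days (57 to 61).

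**Dose dating.** The last listed diary review for completers is T2, nominally day 42 and at latest day 47 (42 + 5). That is before supply could run out ahead of Visit 5.

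**Visit 6 after a gap.** Visit 6 would follow 1 to 7 days of resumed dosing, or up to 7 + 5 = 12 if the ±5-day variance also applies to it.

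**Testing the remedy.** Supplying 33 + 28 = 61 doses leaves no undosed day in any of the 121 pairs under either start day, and also covers the day-62 case (day-1 start, doses on days 1 to 61). Putting the extra five days at Visit 4 instead (28 + 33) still leaves an undosed day before Visit 4 in 44 (day-1 start) or 55 (day-0 start) pairs.

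**The case against.** The strongest reply is that this is a corner case. The 4 to 5 day gap needs near-perfect adherence, Visit 4 on time or early, and Visit 5 at the end of its window. On the plan's own dates, 87 or 81 of 121 pairs have no gap, and a gap of 4 days or more occurs in only 7 or 13. A participant who misses 4 of 60 doses (7%) or 5 of 61 (8%) and keeps the capsules has none. This stands, and it limits the point to something the schedule permits.

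A reader might infer that the primary analysis is compromised. The documents do not support that. The primary measures in Section 8.3 are exhaled NO, superoxide production and xanthine oxidase activity; exhaled NO is repeated and the tissue is taken at Visit 6, after resupply. The methacholine result is not among the outcomes in Sections 4.1 to 4.3. Safety also has other supports in spirometry, repeated ACQ scores and the treatment-failure criteria of Section 9.3. What remains is that the challenge is not repeated, yet it sized the trial and has a stated safety purpose.

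A reader might also infer that the last dose goes unrecorded. That is too strong. The diary card's content is not described and could include dose dates. What the text shows is that no review of it is listed at Visits 5 or 6. In addition, a schedule figure is missing from the text available and might state overage or dose recording.

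**Conclusion.** The mismatch holds on the text. Supply is 56 daily doses, the window lets Visit 5 fall about 5 days after supply ends, and resupply is listed after the Visit 5 tests. At most, the only post-treatment methacholine challenge follows 4 undosed days (day-1 start) or 5 (day-0 start). This assumes no overage, near-full adherence, Visit 4 on time or early, unused capsules kept, and a late Visit 5.

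It does not follow that participants will usually be tested off drug, or that the methacholine result is biased by a known amount. The documents give no washout data and no distribution of visit dates. A longer gap could also be inferred: if leftovers were collected at a Visit 4 on day 23, 28 new doses would last to day 50 and leave days 51 to 60 undosed. No rule for collecting them is stated, so that 10-day figure should not be relied on.

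This is a cheap improvement worth making, not a flaw that undermines the primary analysis. Confidence is medium.

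**What to change.** In Section 6:

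1. Dispense 33 days at Visit 3 and 28 days at Visit 4, and state that participants keep unused capsules. The extra five days belong at Visit 3, where they also prevent a gap before a late Visit 4.
2. Count the 75% rule on days since first dose, not capsules dispensed. Otherwise a fully adherent participant seen on day 23 has taken 22/33 = 67% or 23/33 = 70% of the Visit 3 supply and would be sent to Visit 4A wrongly.
3. Dispense 12 days at Visit 5. Seven is enough only if the plan states that the ±5-day variance does not apply to Visit 6.
4. Record date and time of last dose at Visits 5 and 6, with a diary and capsule check.

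The cost is about five extra days of capsules per participant before Visit 5 (5 × 12 = 60 participant-days), a few more at Visit 5, a reworded compliance rule, and a short added check at two existing visits. No visit is added and the ±5-day window is unchanged.

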### End of Study Visit

If a subject is withdrawn from study participation, an End of Study Visit will be scheduled. This visit will take place at the Asthma Institute and will consist of the following procedures:

- Physical Exam
- Spirometry
- ACQ
- Review of diaries

### Bronchoscopy Procedure (Visits 3 & 6)

Before the bronchoscopy, a tongue scrape will be performed. The subject will be asked to rinse their mouth with saline and spit out the remaining fluid. Using a plastic cell scraper, the subject's tongue will be gently scraped to collect cell samples. Following collection, the samples will be brought to the PI's lab and used to develop cell cultures for research purposes.

The bronchoscopy procedure will take approximately 45 minutes. While in the CTRC, an IV needle will be inserted by CTRC staff and approximately 6 tablespoons of blood will be drawn. The IV will be used to give medications during the bronchoscopy. Depending on the physician's preference, subjects may be given a mild sedative at this time. Subjects will also perform pre and post spirometry in the CTRC and they will be asked to inhale a medicine (albuterol - given via neb) to open up airways.

Once subjects are in the bronchoscopy suite, the nose and throat will be sprayed with lidocaine (a numbing medication or anesthetic) to reduce feeling and coughing. A maximum of 600mg of lidocaine will be used above and below the vocal cords. If the subject has a history of nausea and vomiting from anesthesia, Zofran may be given before the bronchoscopy. Subjects will be given a sedative (Versed-not to exceed 20 milligrams and/or Fentanyl-not to exceed 500 micrograms) in the IV. The subject's respiratory rate will be monitored by pulse oximetry, and

supplemental oxygen will be provided. A bronchoscopy nurse that is specially trained in sedation will do the monitoring and is qualified to administer the sedatives.

Finally, the bronchoscope will be passed into the windpipe. The tube is small enough that the subject can breathe around it, and is designed so that the study doctor can look through it into the lungs. Secretions can be removed by suction through it.

While the tube is in the participant's lung, the following procedures will be performed.

- Pulmonary Lavage. During pulmonary lavage, five 50 cc (a little over 16 Tablespoons) washes of sterile salt-water solution will be injected through the bronchoscope and then immediately sucked out. This allows the doctor to remove some lung cells and secretions for research study. If less than 15cc return from the first 100cc of lavage, the lavage will be stopped.
- Bronchial Brushing. A small brush will be introduced through the bronchoscope and gently rubbed over a very small part of the surface of the lungs. The brush will collect cells, known as epithelial cells, which then can be taken to the laboratory for further study. This is done with 10 brushes.
- Endobronchial Biopsy. While the bronchoscope is inserted, another small instrument will be passed through the bronchoscope to take small samples (biopsies) of tissue from the walls of the airways. Up to 8 samples may be taken during this procedure.

The bronchoscopy procedure will take about 30-45 minutes, but the preparation and recovery time will usually make the visit about 4-8 hours total. If the subject is feeling nauseous after the bronchoscopy, Zofran may be given at the discretion of the physician investigator. An albuterol treatment may be given at the discretion of the physician investigator. Occasionally, the subject's asthma may worsen during or after the procedure. In those cases, we may ask them to spend the night in the Clinical Translational Research Center (CTRC). If subjects are asked to spend the night in the CTRC, subjects will be monitored as described below in the POST Bronchoscopy monitoring procedures.

POST Bronchoscopy Monitoring Procedures:

For this research study, the monitoring/follow-up procedures include:

Subjects will be monitored at UPMC until the sedation has worn off. After the bronchoscopy is completed, subjects will wait in the bronchoscopy recovery area or the clinical research unit for at least 1 hour (but commonly 4-6 hours) following the bronchoscopy to make sure breathing has not been affected by the procedure and to be sure that the anesthesia has worn off. Subjects may be given Tylenol prn if they have a temperature above 38° C. Breathing tests (spirometry) will be done when subjects are awake enough to perform the test and then every 1-2 hours after to make certain breathing capacity is returning to normal level. If subject is not able to breathe as well as before the bronchoscopy we will provide an albuterol dose (can be either neb or MDI) and check spirometry again. If breathing does not return to 85% of baseline after about 6 hours, subject will be evaluated by investigator to determine if further observation (up to 24 hours) is needed. Additional spirometry may be performed for patient safety. It is also possible (if clinically indicated), that subjects receive a prednisone burst to help asthma symptoms improve. However, this is rare since subjects are mild/moderate asthmatics. Subjects will not be allowed to leave the clinic until breathing is back to normal level.

Subjects will not be allowed to drive home after the bronchoscopy. This is because the sedatives used during the procedure may decrease driving ability. We will ask for the contact name and number of the person that will pick up the subject after the bronchoscopy.

The research coordinator will call the subject 24 hours following the bronchoscopy procedure to monitor symptoms. The research coordinator will continue to make follow-up calls as needed for patient safety. At the discretion of the PI, it may be recommended that subjects return to the Asthma Institute for clinical evaluation of breathing issues (respiratory status) in the post bronchoscopy period. This visit would include baseline spirometry and a brief physical exam.

## **7 HUMAN SUBJECTS**

### **7.1 Recruitment and Selection of Patients**

Study participants will be enrolled at Asthma Institute, from clinics, UPMC-affiliated hospitals and communities via various IRB-approved recruitment methods.

### **7.2 Inclusion Criteria**

- 1) Adequate completion of informed consent process with written documentation
- 2) Male and female patients, ≥ 18 - 65 yrs old
- 3) Diagnosis of asthma: based on previous physician diagnosis and either baseline pre-bronchodilator FEV1 50% or greater predicted with a 12% or greater

bronchodilator response to 4 puffs of albuterol or PC20 methacholine (16 mg) if no BD response. If the subject is not currently on an ICS or ICS-LABA combination, PC20 should be < 8 mg, if no BD response. Spirometry results within the prior 24 months located in the subject's medical records can be used to determine eligibility, if available.

- 4) From all racial/ethnic backgrounds with a diagnosis of asthma for  $\geq 6$  months;
- 5) Smoking history  $\leq 10$  pack years and no smoking in the last year;
- 6) BMI  $\geq 30$
- 7) If subject is on ICS or ICS/LABA therapy- 30 days on a stable dose (up to 1,000 mcg daily fluticasone equivalent)

### 7.3 Exclusion Criteria

- 1) Respiratory tract infection within the last 4 weeks;
- 2) Oral or systemic CS burst within the last 4 weeks;
- 3) Asthma-related hospitalization within the last 2 months;
- 4) Asthma-related ER visit within the previous 4 weeks;
- 5) Significant or uncontrolled concomitant medical illness including (but not limited to) heart disease, cancer, diabetes;
- 6) History of ICU admission/intubation due to asthma in the past year;
- 7) More than three systemic corticosteroid requiring asthma exacerbations in the past year;
- 8) Current statins use (statins lower ADMA levels), patients may stop and re-enroll after 2 weeks of stopping statins;
- 9) Positive pregnancy test;
- 10) Intolerance or allergy to the intervention drugs;
- 11) Current or recent participation (within the past 30 days) in an investigational treatment study;
- 12) Unable or unlikely to complete study assessments or the study intervention (i.e. bronchoscopy) poses undue risk to patient in the opinion of the Investigator;
- 13) Any kind of oral nitrates such as nitroglycerin or already taking supplements in this study

- 14) Systemic steroid dependent asthma (no daily oral steroids- short term therapy for asthma exacerbation is permitted)
- 15) Chronic renal failure (creatinine  $\geq 2.0$ ) at screening (associated with higher ADMA levels)- self-reported and/or verified by medical records.
- 16) Use of mouthwash containing chlorhexidine (lowers NO) within 1 week prior to screening and throughout the study.
- 17) Untreated sleep apnea
- 18) Hgb A1C  $\geq 7$ - self-reported and/or verified by medical records.
- 19) Daily use of PPI's (Proton Pump Inhibitor) or H2 Blockers for GERD (it is permitted to take on an occasional basis- no more than 1x per week. If participants wash out of these meds for 1 week, they can enroll)
- 20) Use of biologics for asthma/allergies unless there is a 4 month washout prior to enrollment
- 21) Drug and/or alcohol abuse for  $\geq 1$  year
- 22) Breastfeeding
- 23) Any other condition and/or situation that causes the investigator to deem a subject unsuitable for the study (e.g. due to expected study medication non-compliance, inability to medically tolerate the study procedures, or a subject's unwillingness to comply with study-related procedures.

